After all Pre-testing is complete (including the NP tests), randomization and assignment for LED treatment to Group 1 (Sham 1st, Real 2nd), or to Group 2 (Real 1st, only) will take place. A total of 49 cases are treated per Group; approximately 98 total across the study. The PhD Study Coordinator will use the free computer software program GraphPad (graphpad.com), to assign the participants (10 at a time), using a blocked randomization procedure, into the 2 groups. After 10 participants have been assigned, another set of 10 participants will be randomized into Group 1 or 2 in the same manner. This method will continue to be used, until all cases have been treated, across the study period. The study coordinator at the Boston VA is responsible for assignment of randomization at the SF VA as well.

Participants are treated 2x per week (at least 48 hours between treatments), for 7.5 weeks in each series – total of 15 LED Tx.'s per LED series. **Blinding is preserved** because neither the participant, nor the Neuro-psychologist doing the Pre- Post- testing is aware of whether the patient has received Sham or Real LED.

"Transcranial, Light-Emitting Diode (LED) Therapy to Improve Cognition in GWVI" PI: [name].

Randomized, sham-controlled, study to examine effectiveness of transcranial LED in the near-infrared (NIR) wavelength to improve cognition (Attention, Executive Function, and Memory) in Veterans with Gulf War Veterans' Illness.

Control panel contains 5 switches. They may be used in any combination of On/Off positions.

- 1. On-off
- 2. Front only
- Left only
- 4. Right only
- 5. Midline only

Helmets are made up of 18 Omnilux New-U LED pods.

Omnilux New-U was FDA cleared in 2008 for reducing peri-orbital wrinkles and is sold over the counter.

Each LED pod: Power Output 665.3 mW Power density, 30.8 mW/cm² 20 NIR diodes, 830nm Emitter area: 21.6cm² 1 J/cm² = 32.5 sec 26 J/cm² = 14 min, 5 sec.

Each session, 2 stages: 1. Midline only, 14 m, 5 s 2. R and L sides together, 14 m, 5 s Total Treatment Time = 28 m, 10 s

Clear plastic liner, each case.

The LED Helmet manufactured by PhotoMedex, Montgomeryville, PA will be used (Fig. 19). This helmet contains 18 pods (LED cluster heads). Each pod is 4.5cm x 4.8cm. The helmet is designed with 6 pods to treat the midline of the head; 6 pods to treat the right side of the head; and 6 pods to treat the left side of the head.

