Dotted white lines on MRI in **a.** and **b.**, show expected direction of NIR (870 nm) photons, into bilateral frontal lobes (prefrontal cortex and anterior cingulate gyrus areas), with forehead placements. Additional placement sites are used, see text.

Each placement is applied simultaneously with the helmet during the last 4 min of Part 2 (Left and Right) and for

The chinstrap of the LED helmet will hold the LED cluster heads into place on the front of the L and R ear. All LED cluster heads are wiped with a disinfectant, after each treatment.

All appointments are scheduled ahead, for a specific day and time of day, (usually a Mon/Weds or a Tues/Thurs schedule). It is necessary to have at least 48 hours, between treatments.

If the participant needs to miss an appointment, that appointment will be re-scheduled so that all 15 LED treatments are completed, in each of the two LED treatment series. If a subject misses 2 weeks in a row without any treatment, the subject will be given the option to start over or be withdrawn from the study.

Statistical Analyses and Power Statement [name]; Statistician, VA IRB, Consultant on this project

Participants are likely to show different profiles for performance on individual tests on which they met entry criteria. Using all participants to examine efficacy test by test, will create a serious bias. Therefore, following the lead of the Neuropsychologists on our team ([name] and [name]) we will create 3 cognitive domain scores: Attention/Executive Functioning; Learning and Memory; and Psychomotor/Visual Spatial.

- 1) Attention/Executive Function: Digit Span Subtests (WAIS-IV; Wechsler, 2008); Trail-Making Test (Delis, Kaplan, Kramer, 2001); and Stroop Test ("Color-Word" test) (Delis, Kaplan, Kramer, 2001)
- 2) Learning and Memory: California Verbal Learning Test-II (CVLT-II; Delis, Kramer, Kaplan, & Ober, 2000)
- 3) Psychomotor/Visual Spatial; Continuous Performance Test (Administered on computer; RVisual CPT, NES3) (Letz & Baker, 1988; Rosvold et al., 1956); Rey Osterrieth Complex Figure Test (ROCF) (Knight & Kaplan, 2004)

Each of our individual tests has been standardized, and yields age/education/gender-adjusted z-scores. For each domain, we will compute the mean z-score from those tests that load for that factor (i.e., the two tests selected for Learning and Memory have a total of 9 standardized scores: the domain score will be the mean of these 9 values).

Analysis Plan:

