Preliminary Analyses: Before testing any of the stated hypotheses, the frequency distributions for all study variables will be examined, and appropriate transformations will be carried out whenever violations of normality are determined. Descriptive statistics and bivariate correlations will be computed. This will be necessary in order to test for colinearity among dependent variables. The number of variables will be constrained when r > .75. In addition, each variable will be tested for leptokurtosis to insure that there is a sufficient range of scores. Variables found to be significantly leptokurtic will be converted into dichotomous outcomes.

Tests of Hypotheses: All participants will be evaluated at Entry (Baseline) and within one week of completing either Sham Intervention or Real Intervention The main hypothesis will be tested by two-way mixed-design analysis of variance, with a trend analysis with treatment conditions as the between-groups variable and time of testing as the repeated-measures variable. To control for the fact that the dependent variables can co-vary and for the large number of F-tests to be computed, these analyses will be carried out by Multivariate Analysis of Variance (MANOVA) utilizing PASW v.18. Subsequent to the MANOVA, a series of univariate ANOVAs will be conducted for each dependent variable. Empirical effect sizes will be computed by partial eta². Headsize measurements will be used as covariates.

Power Analysis:

Primary Analysis: The primary analysis is between Real Only and Sham 1st. This comparison will be between groups. It is a parallel design for this primary analysis.

Power and sample size were computed for only the primary, between-group analysis using a moderate effect size appropriate to ANOVA.

The following computer software was used: Borenstein M, Rothstein H and Cohen J. Power and Precision (2004). Englewood, NJ, Biostat. We solved for sample size in order to obtain power = .80 given the following assumptions: alpha = .05 (1-tailed); power = .80; moderate effect size. ANOVA is always a 1-tailed test.

Cohen recommends that readers of his book who consider the ES range defined as 'Large" to be too small (or too large) to meet the appropriate standards of his/her area, should define alternative operational definitions (p.79). See table created below by the PIs from the content in Cohen (1988).

Statistic	ES Index	Small	Medium	Large
Correlation	r	.10	.30	.50

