Difference Between Correlations	q	.10	.30	.50
Proportion equal to .50	g	.05	.15	.25
Difference Between Proportions	ĥ	.20	.50	.80

Chi-Square	W	.10	.30	.50
F Test on Means (ANOVA/ANCOVA) *	f	.10	.25	.40
Multiple Regression	f ²	.02	.15	.35

* Please note, we used **f** as the ES Index for the power calculations submitted to the DMC.

Cohen, J. (1988). Statistical Power Analysis for the Behavioral Sciences (2nd Ed.). Lawrence Erlbaum Associates.

Secondary Analysis:

The Sham 1st shifted to Real will be a second test of efficacy of treatment, and subjects will be compared only within-subject.

In the secondary analyses the two groups will not be compared to one another.

Drop-Outs: In any longitudinal intervention study there will be participants who do not complete the protocol (missing data). The issue of missing data was addressed in a recent special report in the New England Journal of Medicine by an expert panel convened by the National Research Council (Little et al., 2012). Analyses utilizing only data from completers, even when intent-to-treat analyses have established no differences between these samples at Baseline, at best will yield an underestimation of standard errors and, at worst, can lead to biased results. They recommend using an acceptable multiple imputation (MI) procedure to "replace" missing values. Since the data are missing, in all likelihood, Not-At-Random (NAR), this will require generating a model accounting for missingness. Following the recommendations of Moon (Moon et al., 2006) we will utilize a flexible MI procedure known as MICE (multiple imputation by chained equations) on S⁺ and which will utilize the outcome for imputation of missing predictor values. Completers and non-Completers will be first compared on socio-demographic variables to predict the likelihood of completion by discriminant analysis. Any variables that discriminate Completers from non-Completers will be entered into our models as weighted covariates.

Interim Analyses: For both ethical and pragmatic reasons, we have a planned interim analysis at exactly the halfway point of the study, regardless of drop-out rate. To be conservative we will employ the O'Brien-Fleming alpha spending function to establish stopping boundaries. If the MANOVA is significant at p<.022, efficacy will be considered to be reliably established.

Tentative Sequence or Timetable

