If the participant needs to miss an appointment, that appointment will be re-scheduledso that all 15 LED Treatments are completed, in each of the two LED Treatment Series. If a subject misses 2 weeks in a row without any treatment, the subject given the option to start over, or be withdrawn from the study.

k.1.c.1. Therapeutic Risk:

There is no therapeutic risk involved with this project.

k.1.c.2 Research Risk:

There is potential for sleepiness immediately following the first 4 LED treatments. The length of sleepiness may vary from case to case, and if possible an escort will be required, until the patient no longer exhibits excess sleepiness following an LED treatment. We will ask the participant if they feel sleepy. The length of sleepiness may vary from case to case, and an escort will be requested, until the patient no longer exhibits excess sleepiness following an LED treatment. They will not be excluded from the study if they cannot bring an escort as requested. If they do not bring an escort and they report feeling sleepy, they will be asked to remain for an hour. If the participant prefers to leave that will be their choice.

k.2 Adequacy of Protection from Risk

k.2.a Recruitment and Informed Consent

Only GW veterans will participate; 98 over the grant period. All potential treatment study participants were advised in their prior informed consent procedures for previous VA-related GW studies that they may be contacted in the future about the possibility of participating in future studies. Veterans will be recruited for this study through the Co-Investigator, [name]., Clinical Neuropsychologist, VA Boston Healthcare System.

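### Randomised participants who miss two weeks and do not restart leave the study untested, and the planned imputation does not fully repair the loss

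*Combined protocol and SAP*

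**What the plan says.** The missed-appointment rule closes section 2a. 3b (Method of Transcranial LED Treatment). A single missed visit is made up: "that appointment will be re-scheduled so that all 15 LED treatments are completed". The next step begins "If a subject misses 2 weeks in a row without any treatment", and then "the subject will be given the option to start over or be withdrawn from the study". Section k.1.c repeats it in almost the same words: "the subject given the option to start over, or be withdrawn from the study".

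Four other places bear on the consequence:

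- **Randomisation.** Section 2a. 3b puts it before any treatment: "After all Pre-testing is complete (including the NP tests), randomization and assignment for LED treatment".
- **Outcome testing.** Tests of Hypotheses says "All participants will be evaluated at Entry (Baseline) and within one week of completing either Sham Intervention or Real Intervention". The flowcharts in section 2a. 3 count T2 (within 1 week) and T3 (1 month) from the 15th treatment.
- **Recruitment.** Section 2a. 3 gives about 49 per group, 98 in total. Section k.2.a keeps recruitment open until 98 people have completed.
- **Missing data.** The Drop-Outs paragraph warns about "Analyses utilizing only data from completers, even when intent-to-treat analyses have established no differences" and says such analyses can be biased. It adds: "Since the data are missing, in all likelihood, Not-At-Random (NAR), this will require generating a model accounting for missingness". It names multiple imputation by chained equations (MICE), after comparing completers and non-completers on socio-demographic variables.

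**The concern.** The only alternative to restarting is to leave the study, not merely to stop treatment. Everyone who reaches that choice in the first series is already randomised. Post-testing is timed from the 15th treatment, and no section provides testing for someone who stops earlier, so a participant who chooses withdrawal has a baseline score and nothing after it.

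A two-week gap could well be related to how the person feels or whether they notice benefit. The Drop-Outs paragraph takes the same view when it calls missingness probably not at random. The groups that are tested may then no longer be the groups that were randomised.

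The restart option raises a smaller, separate gap. Restarted participants stay in the trial, but they are tested later and after more than 15 sessions in total, and the plan does not say how they are analysed.

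**Working it through.** **1. Who has no outcome.** The sections are read in order: randomised after baseline testing (2a. 3b); two weeks missed, restart declined, withdrawn from the study (2a. 3b, k.1.c); T2 and T3 timed from the 15th treatment (2a. 3), with no alternative date. Result: no T2 or T3 score. This applies to the withdrawal branch only.

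**2. The plan's own sample size.** Inputs from Power Analysis: alpha 0.05 one-tailed, power 0.80, moderate effect. Its table gives f = 0.25, which is d = 2 × 0.25 = 0.5 for two equal groups.

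- n per group = 2 × (1.645 + 0.842)² / 0.5² = 49.5, rounded up to 50, against the stated 49.
- One-sided t test at 49 per group: non-centrality 0.5 × √(49/2) = 2.47, power 0.79.

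The figure reproduces on the one-tailed basis, with no allowance for drop-out.

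**3. Power if 98 is the number randomised.** The documents give no rate, so 10% and 20% are assumed, spread evenly over the arms.

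| Untested | Tested per arm | Power (one-tailed) | Randomise to have 98 tested |
|---|---|---|---|
| 0% | 49 | 0.79 | 98 |
| 10% | 49 × 0.90 = 44.1 | 0.75 | 98 / 0.90, i.e. 109 |
| 20% | 49 × 0.80 = 39.2 | 0.71 | 98 / 0.80, i.e. 123 |

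If leavers are replaced, as k.2.a implies, the number tested returns to about 98 and this loss largely disappears.

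**4. Bias of an analysis of tested participants.** This is a different scenario from step 3. Let w be the untested share of an arm and g the untested-minus-tested mean difference in SD. The bias in Real minus Sham is w(Sham) × g(Sham) − w(Real) × g(Real).

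- Real arm only, w = 0.10, g = −0.3: bias = 0.10 × 0.3 = +0.03 SD.
- Real arm only, w = 0.20, g = −0.5: bias = 0.20 × 0.5 = +0.10 SD.
- Sham arm only: the same sizes with the opposite sign.
- Equal w and equal g in both arms: zero.

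Against the planned 0.5 SD, 0.03-0.10 SD is 6-20% of the effect. Replacement does not change this, because new recruits do not supply the missing scores.

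**5. What MICE can recover.** In its standard form it assumes data are missing at random given the variables in the model. The plan expects otherwise, says a missingness model is needed, and then specifies neither a not-at-random model nor a sensitivity analysis. Someone withdrawn before T2 contributes only baseline cognitive scores.

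**6. Restart, extreme case.** A gap straight after session 14 gives 14 + 15 = 29 sessions. T2 falls 7 + 2 + 7.5 = 16.5 to 17.5 weeks after the start, against 7.5 to 8.5 weeks on schedule.

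**The case against.** The plan is more careful than the rule alone suggests. Missed visits are rescheduled first, the rule applies only after two full weeks, and restarting keeps the person in testing. The choice is the participant's, and section 2a. 3a. ia allows withdrawal at any time, so some of these scores would be lost under any rule. The Drop-Outs paragraph rejects completer-only analysis and names an imputation method. All of this stands, and it limits the size of the problem.

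Three stronger readings are tempting, and the documents do not support them:

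- **That the rule turns the trial into a completers-only analysis.** It does not: MICE is planned. What remains is that MICE as described does not fit the missingness the plan expects.
- **That 10-20 of 98 outcomes are certainly lost, with power falling from 0.69.** No rate is given, and k.2.a implies replacement. The 0.69 is the ordinary two-group F test at 49 per arm. Its distance from 0.80 comes from the one-tailed assumption, a separate matter that this rule does not cause.
- **That bias is shown.** Its direction and size depend wholly on assumed shares and differences, and it may be zero.

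The 29-session restart is likewise an extreme that the text permits, not an expected course. Restarts are unspecified, not shown to be wrong.

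**Conclusion.** The point holds in limited form. As written, a randomised participant who declines to restart and is withdrawn before finishing the series has no T2 or T3 score. Replacement restores numbers but not the randomised comparison, and the imputation described does not fully repair the loss. How restarted participants are analysed is left open.

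The size cannot be fixed from the documents. On the assumptions shown, the cost is either a fall in one-tailed power from 0.79 to about 0.75-0.71 (98 randomised, 10-20% untested evenly, no replacement) or a bias of 0.03-0.10 SD (10-20% of one arm only, 0.3-0.5 SD worse, tested participants analysed). These are separate scenarios and should not be combined. The first largely vanishes with replacement; the second vanishes if withdrawal and score differences are the same in both arms. The change is worth making because it is cheap, not because serious bias has been demonstrated.

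**What to change.** Leave the treatment rule as it stands, and separate stopping treatment from leaving the study.

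- **Those who stop.** Unless consent to follow-up is withdrawn, invite them to T2 and T3 on the dates the planned schedule would have given, counted from first treatment: about 7.5 + 1 = 8.5 weeks for T2, and 7.5 weeks plus one month, about 11.5-12 weeks, for T3. Include them in their assigned arm in the primary analysis.
- **Those who restart.** Test them after the 15th session of the restarted series and analyse them as randomised. Record actual sessions and test dates, and run a sensitivity analysis that excludes them.

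The cost is protocol wording and up to two extra test visits per affected participant, of a kind already in the schedule. The documents show no budget, so funding for them cannot be assumed. Those who stop will be tested on a different clock from those who finish, and some will decline, so the missing-data plan is still needed.

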For repeated administrations of the trailmaking test, the Trails Test from the D-KEFS (trials 1-5) will used. The D-KEFS (Delis, Kaplan & Kramer, 2001) is a nationally standardized set of nine tests that measures a wide range of verbal and nonverbal executive functions. Each test is designed to be a stand-alone instrument that can be administered individually or along with other D-KEFS tests. In clinical populations, the D-KEFS can be used to assess mild brain damage in general and mild frontal-lobe involvement in particular.

Stroop Color-Word Interference Test (Stroop): The Stroop Color-Word Test is a brief, five minute test used to evaluate aspects of executive functioning, including cognitive flexibility, resistance to interference from outside stimuli, and creativity (Golden, 1978). EEG and functional neuroimaging studies of the Stroop effect have consistently revealed activation in the frontal lobe, more specifically in the anterior cingulate cortex and dorsolateral prefrontal cortex (Carter & van Veen, 2007). Four trials of the Stroop Test from the D-KFES will be administered both as a screening and an outcome measure. If the subject screens into the study based on the initial NP screening, the test is not re-administered for Baseline data; and the scores are pulled over from the NP screening, and entered as Baseline data.

California Verbal Learning Test-II (CVLT-II): The CVLT-II assesses multiple aspects of verbal learning (Delis et al., 2000). CVLT-II administration requires that a list of 16 words be presented to the examinee for memorization (4 words from 4 categories: furniture, vegetables, ways of traveling, and animals). The CVLT-II

measures both recall and recognition of the word lists over 5 different trials. It also measures delayed and cued recall. The CVLT-II has alternate forms for repeated administrations. The scores from the CVLT-II will be used for screening and as a primary outcome measure. If the subject screens into the study based on the initial NP screening, the test is not re-administered for Baseline data; and the scores are pulled over from the NP screening, and entered as Baseline data.

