Continuous Performance Test-Visual AX version (CPT): The CPT measures a person's impulsivity, selective attention, plus sustained attention and effort in a cognitively demanding context. The computerized presentation of the visual CPT-AX version in this study (NES; Letz & Baker, 1988) will require the examinee to respond with a right mouse press whenever the letter stimulus on screen is an X that was preceded in the sequence by the letter "A". The left mouse button is pressed for an X that was not preceded in the sequence by the letter "A". Stimuli are presented for 200 msec each. The inter-trial interval varies across trials and may be 1.5, 2.0 or 2.5 seconds (this includes the duration of the stimulus), so the average ITI is 2.0 seconds. Approximately 20% of the stimuli are targets (A preceding X). Performances will be scored for: % correct target detections, % non-target detections, false alarms, reaction times. The CPT can be repeatedly administered.

Rey-Osterrieth Complex Figure Test (ROCF): The Rey–Osterrieth Complex Figure Test (ROCF; Osterrieth, 1944; Rey, 1941)is a widely used neuropsychological test for evaluating visuospatial-visuoconstruction ability and visual memory (Knight and Kaplan, 2004). It has also been used for measuring executive functions mediated by the prefrontal cortex. Examinees are asked to reproduce a complicated line drawing as a direct copy and from memory. The ROCF involves three test conditions: Copy, Immediate Recall and Delayed Recall. Each of the three productions generated is scored for accuracy and placement of 18 specific design elements according to established scoring rules. The ROCF test will be used an outcome measure.

Controlled Oral Word Association Test (COWAT)-FAS Test (Screening only): The COWAT is a brief and sensitive measure of executive function. The version used in this study appraises verbal fluency by requiring the examinee to generate as many words as possible in 60 seconds beginning with a specific letter F, A, or S. The examinee's scores is the Total Number of Words generated across the three letter categories. Both frontal and temporal lobe areas of the brain have been implicated by neuropsychological investigations as being involved in successful performances (Lezak, 1995).

2a. 3a. ii. Primary Outcome Measures, Neuropsychological Tests

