The neuropsychological tests cover 3 cognitive domains: 1) Attention/Executive Function; 2) Learning and Memory; and 3) Psychomotor/Visual Spatial. A sample data entry sheet for NP tests is provided in Appendix 4.

1) Attention/Executive Function

Digit Span Subtests (WAIS-IV; Wechsler, 2008)

D-KEF Trails (Delis, Kaplan & Kramer, 2001)

Stroop Test ("Color-Word" test) (Delis, Kaplan & Kramer, 2001)

2) Learning and Memory

California Verbal Learning Test-II (CVLT-II; Delis, Kramer, Kaplan, & Ober, 2000)

3) Psychomotor/Visual Spatial

Continuous Performance Test (Administered on laptop computer; RVisual CPT, NES) (Letz & Baker, 1988; Rosvold et al., 1956)

Rey Osterrieth Complex Figure Test (ROCFT; Knight & Kaplan, 2004)

2a. 3a. iii. Secondary Outcome Measures

These additional tests measure other symptoms associated with GWVI. Sample data entry sheet, App. 4. Pain Tests: VAS Pain Scale (0-10) (Farrar et al., 2001); Short Form McGill Pain Questionnaire (Melzack, 1984); and the West Haven-Yale Multi-dimensional Pain Inventory (WHYMPI, Kerns et al., 1985). Fatigue: Multi-Dimensional Fatigue Inventory (Smets et al., 1995).

Sleep: Pittsburgh Sleep Quality Index (PSQI) (Buysee et al., 1989). Karolinska Sleepiness Scale (KSS). The Karolinska Sleepiness Scale will be administered each of the Neuropsychological Testing time points and each treatment day, at the end of treatment.

Actigraphy (Actiwatch): Accelerometer worn on the wrist as a watch used to provide an objective sleep measure; worn 1 week at a time, pre- treatment, 1 week and 1 month, post- Real and Sham LED treatment series. A sleep log will be filled out each week the Actiwatch is worn.

Mood: Beck Depression inventory (BDI; Beck, 2006)

Data for General Physical Health: Short Form-36V Plus (Ware et al., 2000); and the Health Symptom Checklist (HSC). The HSC is a comprehensive list of 34 frequently reported health and mental health symptoms originally adapted from Bartone et al., (1989). It asks how often in the past 30 days each of the

health symptoms was experienced. Symptoms from nine body systems are assessed (cardiac, pulmonary, dermatological, gastrointestinal, genitourinary, musculoskeletal, neurological, and psychological). 2a. 3b. Method of Transcranial LED Treatment

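### The Learning and Memory score rests on a one-test list and a two-test scoring sentence, and a conditional rule to dichotomise leptokurtic variables reaches the primary domain scores at some cost in power

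*Combined protocol and SAP*

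**What the plan says.** **Domain score.** Section 2a.3a.ii (Primary Outcome Measures) and the domain list in Statistical Analyses and Power Statement agree. Three domains are formed, and the second reads "Learning and Memory: California Verbal Learning Test-II", with nothing else beside it. The general rule that follows is that "we will compute the mean z-score from those tests that load for that factor". The illustration attached to that rule then states that "the two tests selected for Learning and Memory have a total of 9 standardized scores" and makes the domain score the mean of those nine.

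The CVLT-II description says the test "measures both recall and recognition of the word lists over 5 different trials", plus delayed and cued recall, but does not say which of these are averaged. The Rey-Osterrieth figure (ROCF) is described as "evaluating visuospatial-visuoconstruction ability and visual memory", and "The ROCF involves three test conditions: Copy, Immediate Recall and Delayed Recall". Both domain lists place it under Psychomotor/Visual Spatial. On itemisation the text says only that "A sample data entry sheet for NP tests is provided in Appendix 4".

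**Dichotomising rule.** Preliminary Analyses first calls for the distributions of all study variables to be examined and for transformation where normality fails. It then has each variable tested for leptokurtosis, to make sure the scores have enough range, and turns the significantly leptokurtic ones into two-category outcomes. It gives no test level, visit, cut-point or binary model, and does not say whether kurtosis is tested before or after transformation.

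**Primary test.** Tests of Hypotheses specifies a mixed-design ANOVA (treatment between groups, time repeated), carried out as a MANOVA, on baseline and the visit within one week of the series. Power Analysis sizes it with the index f.

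**The concern.** The cognitive tests are the primary outcomes, and the three domain scores are how they are analysed. If one domain's content is stated in two incompatible ways, two analysts can follow the text and compute different scores. The planned interim MANOVA would then rest on whichever score was chosen.

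The dichotomising rule is a separate matter. The primary comparison and its sample size are about means of continuous scores. A rule that replaces a heavy-tailed score with a 0/1 variable discards information in a setting where a rank test would usually hold or gain power. Because the visit and cut-point are open, the analyst has to settle them after seeing the distributions.

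**Working it through.** **1. Domain score: the statements side by side.**

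| Place | Learning and Memory contains |
|---|---|
| Section 2a.3a.ii | CVLT-II |
| Statistical Analyses, domain list | CVLT-II |
| Statistical Analyses, general rule | mean z-score of the tests that load |
| Statistical Analyses, illustration | mean of 9 scores from two tests |

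The first three rows are consistent and give a CVLT-II mean. The fourth cannot be carried out without guessing a second test. Reading it as one test does not finish the job, because the nine scores are not listed in the text. An effect on power would require the number of scores per test, their correlations and the second test's response to treatment. The documents give none of these, so no figure is offered.

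**2. The plan's own sample size.** With f = .25 (medium in the plan's table), d = 2f = .5. At one-sided .05 and power .80:

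n per group = 2 × [(1.645 + 0.842)/0.5]² ≈ 49.5, rounded up to 50.

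This agrees with the stated 49 to within one per group, and it treats the outcome as continuous. At 49 per group, power is .79–.80 one-sided. It is .69 two-sided, which for two groups is the ANOVA F test at .05 and is the reference level below. (The choice of sidedness is a separate issue.)

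**3. Simulation when the rule fires.** The documents give no distributions or correlations, so these are assumed:
- single score = common part + visit-specific part, each t(8), t(5) or Laplace
- retest r = .5–.7
- 49 per arm, change d = .5, two-sided .05
- SD of change = √[2(1 − r)], so the shift is .50 at r = .5 and .39 at r = .7 in score SDs
- flag = kurtosis test z > 1.96 on the 98 scores pooled over arms (level assumed)
- split at the baseline median at both visits

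Power where both visits are flagged:

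| Analysis of change | Power |
|---|---|
| t-test, continuous | about .65–.69 |
| rank test | about .66–.74 |
| baseline-median split | about .35–.49 |

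The two visits' flags disagree in about 21–43% of trials, so it matters which visit triggers conversion.

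**4. Loss over all trials.** Overall loss = P(rule fires) × (t-test power − split power, given that it fires).
- Simulated: about 1–9 points if both visits must be flagged; about 7–19 if either flag suffices.
- Rough check of the first range: in a 20,000-run version that also included shared-scale tails, both visits were flagged in 960 to 6,000 trials per cell, that is 4.8% to 30%. The conditional gap is .69 − .49 = .20 to .65 − .35 = .30. The products run from 0.048 × .20 = 1.0 point to 0.30 × .30 = 9.0 points.
- Normal data: simulated, about 0–1 point. By hand at r = .5, the flag rate is .0245 per visit and power goes from .68 to .37. With independent flags, both visits give .0245² × .31 = 0.02 points, and either gives [1 − (1 − .0245)²] × .31 = 1.5 points, which is the same order.

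**5. Where the loss is small.**
- Mean of 9 scores (inter-score r .3–.5, both visits flagged, no transformation): t(8) about 0.5–2.6 points, t(5) 3–6.5, Laplace (r = .5 only) 2–2.6.
- Three-domain MANOVA (Hotelling T², inter-domain r = .5, one domain flagged at both visits and split, all three benefiting): .68–.76 against .71–.77 continuous.
- Scores at ceiling in 60%/80% of people: t-test .31/.18, rank .32/.19, binary .29/.19, so no material loss.

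**The case against.** **On the domain score.** Two matching lists name the CVLT-II alone. The conflict sits in one parenthesis illustrating a general rule that works without it, and a leftover count is at least as likely as a missing test. Appendix 4, which is not available here, may itemise the nine scores. All of this stands, and it makes the point a correction rather than a flaw of design. The appendix still cannot turn one listed test into two.

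A reader might infer that the ROCF is the missing test, since it has recall conditions. The documents do not say so, and both lists put it elsewhere. Simulated powers for a domain with some scores from a second test would only measure the invented split of scores.

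**On the dichotomising rule.** It applies only to variables found significantly leptokurtic. Its stated purpose, enough range of scores, suggests clustered scores, for which splitting costs nothing. A transformation applied first might also stop it firing. These points stand and bound the size.

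A reader might infer that a flag at one visit leaves the group-by-time comparison undefined. The text does not support that: a mixed ANOVA can be computed on 0/1 scores, and with time as a repeated factor a variable can naturally mean the measure at both visits. One-visit conversion is something the plan leaves unaddressed, not something it prescribes.

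A reader might also infer a large loss in the MANOVA. That needs benefit confined to the split domain (.24–.47 against .63–.66 continuous), which the plan does not assume.

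**On timing.** The document is dated December 2017, 50 Boston cases were projected for September 2017, and half of 98 is 49. The interim may already have taken place; the documents do not say.

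**Conclusion.** Both points hold and should be fixed. The contradiction over Learning and Memory is plain in the text and affects a primary score. Its consequence for power is unknown, and the likeliest explanation may be leftover wording.

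The dichotomising rule, as worded, reaches the primary domain scores and works against a test built on means. Its cost is conditional. When it fires at both visits on a heavy-tailed single score, power falls from about .65–.69 to about .35–.49. Averaged over all trials the loss is moderate or small, and it depends on whether both flags or either flag triggers conversion, which the plan does not state. It shrinks further for a nine-score mean and for the MANOVA when all domains benefit.

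These sizes rest on the assumed tails, retest correlations, effect and flag level. The two defects of wording do not. Nothing in the documents suggests that outcomes would be chosen on treatment results.

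**What to change.** 1. List the standardised scores that enter each of the three domains, and correct the sentence about two tests and nine scores to match.
2. For the three primary domain scores, remove the dichotomising rule. Keep them continuous, with any transformation applied identically at both visits. Pre-specify a rank or permutation version of the Real versus Sham comparison for use if residuals remain heavy-tailed.
3. Make both changes before any further look at data by arm (before the interim, if it has not yet occurred) and record the date.

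The cost is SAP wording and one short additional analysis, with no new data. The downside is that a rank result is less directly expressed as partial eta-squared, the plan's effect measure.
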